1.10 Risks, burdens and benefits

1.10.1 Phase 1

1.10.1.1 Risk

There is minimal risk to patients participating in phase 1 of the study. A trans-rectal ultrasound examination of the prostate will be performed prior to any standard care being undertaken. The standard care for patients with MRI PI-RADS score 3, 4 or 5 is to have a transrectal ultrasound probe inserted into the rectum, the prostate identified and appropriate biopsy sites determined. The majority of men tolerate this procedure well. The multi-parametric US examination will involve a probe being inserted into the rectum, images taken and stored for evaluation later. The probe will then be withdrawn and standard care will commence.

1.10.1.2 Burden

The burden upon the patient is to have two probes separately inserted into the rectum as opposed to once for standard care. The examination time will be extended by a maximum of 10 minutes. The burden is greater for participants with MRI PI-RADS score of 1 or 2. Rectal ultrasound and biopsy is not indicated as part of their standard care pathway and, as such, participation in the study will include a transrectal ultrasound examination that they would not normally receive. Both examinations will take no more than 10 minutes in total and will be planned around clinic attendances to avoid unnecessary visits to the hospital.

1.10.1.3 Benefit

The benefit is that the researcher will gain valuable data in terms of stored ultrasound images that can be correlated to existing gold standard MRI and histology where available. The patients will have the satisfaction of participating in a study evaluating new technology which may lead to better outcomes for future patients. The ultrasound imaging is unlikely to be able to provide diagnostic or prognostic information until a comparative analysis with the gold standards has been performed. However, should any findings of incidental pathology or suspicious appearances be determined during the ultrasound examination these will be alerted to the lead clinician. Any such incidental or suspicious findings will then be discussed at the urology multi-disciplinary meeting (MDT) to determine a management plan. Such findings may result in early detection of potential issues providing a benefit to participants on this study.

1.10.2 Phase 2

1.10.2.1 Risk

There is minimal risk to patients participating in phase 2 of the study. A trans-rectal ultrasound examination of the prostate will be performed prior to any standard care being undertaken. Standard care includes a PSA blood test and a DRE. A multi-parametric US examination will be performed immediately following the regular DRE. It again will involve a probe being inserted into the rectum, images taken and stored for evaluation later. This will be repeated with the micro ultrasound probe. The probe will then be withdrawn and the patient attendance complete. Both examinations will take no more than 10 minutes in total.

1.10.2.2 Burden

There is a greater burden to phase 2. This is an examination over and above standard care. The patient will need to tolerate a rectal ultrasound examination every 6 months. As this new technology is being investigated it is not a diagnostic examination and will not provide diagnostic or prognostic results for the individual participant. The burden of dealing with the unknown will be explained to the participant and access to urology specialists will be available at all times. Should any findings of concern be detected on evaluation of the multi-parametric US these will be alerted to the lead urologist and arrangements for MRI will be made. Any changes on MRI compared to the baseline imaging will necessitate diagnostic biopsy.

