1.5.2 Eligibility criteria in clinical practice

MRI is offered to all men who meet the eligibility criteria of age ≤ 75 , PSA ≤ 20 and life expectancy of ≥ 10 years. MRI is reported using the PI-RADS V2 criteria; a 5 point scale with 1 & 2 highly unlikely to have significant prostate cancer, 4 & 5 highly likely to have significant prostate cancer and PI-RADS 3 equivocal and further investigation warranted. The pathway in the Hull University Teaching Hospitals NHS Trust is that patients with PI-RADS score of 1 or 2 are not routinely offered biopsy due to the risk of biopsy complications being greater than the likelihood of prostate cancer. Men meeting these criteria will be invited to participate in phase 1 of the study and the multi-parametric US will be correlated with MRI only. A biopsy will not be performed. Any men from this cohort electing for AS will be invited to join phase 2.

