1.5.14 Data analysis

Once the database is complete for each participant, the lead researcher will compare the:

- ultrasound scores
- ultrasound colour Doppler findings
- prostate volume size
- lesion size

The above criteria will be compared between both the standard and micro-US imaging, and then the standard and micro-US with both MRI and histology. An assessment of agreement will be undertaken to evaluate the concordance between the two reviewers of the same images (Ranganathan, Pramesh and Aggarwal 2017). The relationship between these pairs will be evaluated using Bland-Altman plots. Scores from the ultrasound reviews will also be evaluated to determine inter-and intra-operator agreement between the randomly allocated reviewers. The inter-rater reliability, both within and across subgroups of reviewers, will be assessed using the intra-class correlation coefficient or the Cohen weighted kappa test (de Raadt et al. 2021).

1.6 Study design and methodology – Phase 2

Men eligible for AS will be invited to participate in phase 2. A multi-parametric US examination will be undertaken as part of the AS monitoring regime. Men under AS have a prostate serum antigen (PSA) blood test and digital rectal examination every 6 months. A multi-parametric US examination will be undertaken at these appointments to minimise unnecessary health care interactions for the participants. The multi-parametric US examination will be performed blinded to the previous examinations and histology results. The images will be scored and then correlated with previous imaging scores and current PSA levels. Any changes will be indicated to the lead urologist and the patients will be offered MRI imaging to evaluate any changes using existing gold standard imaging.

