1.6.1 Phase 2 recruitment

Participants into phase 2 of the study will be invited from the cohort of patients who have already undergone investigations for suspected prostate cancer which include MRI imaging as a requisite. Patients who have low probability MRI scores of PI-RADS 1 or 2 will be invited onto the phase 2 longitudinal arm of the study. Patients who have had biopsy and have either low risk localised

prostate cancer and have elected to be monitored with AS, or those with higher grade disease and who have elected to be monitored via a WW pathway will also be invited on to the phase 2 longitudinal arm of the study.

1.6.2 Sample size phase 2

Again, determining a sample size for this proof of concept study remains difficult. Given the small numbers likely to be recruited into phase 1 and therefore eligible to continue to phase 2, all phase 1 participants who are managed under AS or WW will be invited to continue onto phase 2 of the study with maximum cohort of 30 being accepted. It is acknowledged that inclusion in phase 2 is dependent upon cancer grading at diagnosis and, due to uncertainty of disease diagnosis within the cohort it may be difficult to recruit participants within the two-year time limit for data collection. Participants in phase 1 and 2 will continue to be recruited up to a maximum of 18 months from the commencement of the study to maximise the opportunity for phase 2 recruitment.

1.6.3 Inclusion criteria for phase 2

Men referred to urology within Hull University Teaching Hospitals NHS Trust with known localised prostate cancer of Gleason 3 + 3 (6) or less and:

- Are eligible for an AS monitoring pathway
- Are on an AS monitoring pathway which is regularly reviewed by a consultant urologist
- Able to attend Castle Hill Hospital for 6 monthly multi-parametric US examinations
- Are able to tolerate a rectal ultrasound examination
- Able to provide informed consent to the study

1.6.4 Exclusion criteria for phase 2

- Men who meet eligibility criteria for active surveillance but have elected to undergo active treatment (hormone treatment, prostatectomy or radiotherapy)
- Men who do not meet eligibility criteria for active surveillance
- Men who are eligible for inclusion but who cannot tolerate rectal ultrasound examinations.
- Men who are unable to consent to the study
- Men who withdraw consent during the longitudinal study
- Men who are unable to attend Castle Hill Hospital for ultrasound imaging within study time frames

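### The phase 2 rule that any MRI change leads to biopsy has no direction or level and is not reconciled with section 1.5.2, the MDT route or the phase 2 risk statement

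*Protocol*

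**What the plan says.** **Biopsy after a phase 2 MRI (1.10.2.2 Burden).** "Any changes on MRI compared to the baseline imaging will necessitate diagnostic biopsy". No direction, size or PI-RADS threshold is attached.

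**What leads to that MRI.** Section 1.10.2.2: "Should any findings of concern be detected on evaluation of the multi-parametric US these will be alerted to the lead urologist and arrangements for MRI" follow. The introduction to section 1.6 words it differently: "Any changes will be indicated to the lead urologist and the patients will be offered MRI imaging". In both places the study ultrasound starts the sequence.

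**PI-RADS 1 and 2 in the local pathway (1.5.2).** "patients with PI-RADS score of 1 or 2 are not routinely offered biopsy", and the reason given is "due to the risk of biopsy complications being greater than the likelihood of prostate cancer". The same section treats PI-RADS 3 as equivocal and calling for further investigation.

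**Entry to phase 2.** Section 1.6.1: "Patients who have low probability MRI scores of PI-RADS 1 or 2 will be invited onto the phase 2 longitudinal arm of the study". Section 1.5.2 narrows this to men of that group who elect for active surveillance (AS). Section 1.6.3 requires known localised cancer of Gleason 6 or less.

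**Who decides.** Section 1.6.10 has a man with a changed ultrasound score reviewed at the next MDT. Section 1.10.2.3 has the MDT settle the plan after incidental or suspicious ultrasound findings.

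**Risk (1.10.2.1).** "There is minimal risk to patients participating in phase 2 of the study". The paragraph goes on to describe the probe examinations and does not mention biopsy.

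**The concern.** Phase 2 monitoring outside the study consists of six-monthly PSA and digital rectal examination (section 1.6). The study adds an ultrasound, which can prompt an MRI, and 1.10.2.2 makes any change on that MRI lead to biopsy. A biopsy reached this way follows from taking part, although an MRI change must come in between.

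The wording leaves no discretion and sets no threshold. It therefore catches a repeat MRI that has changed but still reads PI-RADS 1 or 2, the range in which 1.5.2 gives a reason for not routinely offering biopsy. It also catches an MRI that has improved.

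At stake is an invasive procedure. Clinicians at the site could reach different decisions for the same man depending on which section they follow, and a participant or ethics reviewer who reads only the risk paragraph would not learn that biopsy is a possible consequence.

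**Working it through.** No sample size, power or error rate is involved, and the protocol states no figure to reproduce. The check sets the sections side by side and counts the possible score changes.

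**Step 1. Possible changes on the five-point PI-RADS scale** (scale from 1.5.2). Ordered pairs of baseline and follow-up score: 5 × 5 = 25. Unchanged pairs: 5. Changes: 25 − 5 = 20. As worded, 1.10.2.2 applies to all 20. It would also apply to a change that leaves the score the same, for example in lesion size.

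**Step 2. Sort the changes by what 1.5.2 says about them.**

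| Baseline | Follow-up | Count | Relation to 1.5.2 |
|---|---|---|---|
| 1 or 2 | 1 or 2 | 2 (1 to 2, 2 to 1) | Its stated reason applies; at odds with 1.10.2.2 |
| 1 or 2 | 3, 4 or 5 | 2 × 3 = 6 | Reason no longer applies; no conflict |
| 3, 4 or 5 | 1 or 2 | 3 × 2 = 6 | Score is in the range, but the cancer is normally already diagnosed; not addressed |
| 3, 4 or 5 | lower, still 3 or more | 3 (4 to 3, 5 to 3, 5 to 4) | Not addressed |
| 3, 4 or 5 | higher | 3 (3 to 4, 3 to 5, 4 to 5) | No conflict |

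Total: 2 + 6 + 6 + 3 + 3 = 20. These are logical possibilities and not frequencies; the protocol gives no rate for any of them.

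**Step 3. Why the third row is separate.** The reason in 1.5.2 weighs complications against the likelihood that cancer is present. Under 1.6.1, men who are not at PI-RADS 1-2 reach phase 2 after a biopsy, with low-risk cancer on AS or higher-grade disease on watchful waiting. For them the presence of cancer is already known, so the reason does not carry over cleanly. Section 1.10.2.2 still demands biopsy when their score falls, and nothing elsewhere says whether that is intended.

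**Step 4. Can the first row occur?** Under 1.6.1, yes: PI-RADS 1-2 men are invited. Under 1.6.3, a man without a biopsy has no known cancer and does not qualify. The protocol does not say which section governs. The first row therefore depends on an unresolved eligibility question. The falls in score do not, because a man at baseline PI-RADS 3 to 5 with Gleason 6 disease on AS meets 1.6.3.

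**Step 5. Who decides.** Sections 1.6.10 and 1.10.2.3 refer ultrasound changes and suspicious findings to the MDT. Section 1.10.2.2 fixes the later step, from MRI to biopsy, as automatic. The protocol does not say whether the MDT's decision extends to it.

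**The case against.** The strongest reply is that 1.5.2 and 1.10.2.2 address different situations. Section 1.5.2 describes the Trust's routine pathway after the first diagnostic MRI. It states a default and not a bar, and it is silent on a follow-up MRI that has changed in a man whose ultrasound also raised concern. This largely stands. A reader might infer that the protocol flatly contradicts its own benefit-risk statement; the text does not support that. It does show a stated reason for not routinely offering biopsy at PI-RADS 1-2 and, elsewhere, a mandatory rule that ignores the reason.

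A reader might also count every change ending at PI-RADS 1 or 2 (2 + 6 = 8 of 20), or every change that is downward or ends there (6 + 3 + 2 = 11 of 20), as a conflict. Neither count is supported. Six of the 8 start from PI-RADS 3 to 5, where cancer has normally been diagnosed already, and 1.5.2 does not speak to downward moves as such.

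Section 1.4.2 says phase 2 looks for changes that may indicate progression, so the authors may have meant only adverse changes. That is plausible, but the sentence does not say so.

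Finally, biopsy is disclosed: it appears under Burden, directly after Risk, within section 1.10. It would be wrong to say that the protocol hides it. What remains is that the paragraph rating the risk leaves it out.

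**Conclusion.** The point holds as a matter of reconciliation. The biopsy rule in 1.10.2.2 has no direction or level. Read literally, it is at odds with the reasoning in 1.5.2 for MRI changes that stay within PI-RADS 1-2 (two of the 20 possible score changes), and it extends to downward changes in diagnosed men, which no other section covers. It is not aligned with the MDT route or with the minimal-risk statement.

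The number of men affected is unknown and cannot exceed the phase 2 maximum of 30. The clearest clash assumes that 1.6.1 governs entry; if 1.6.3 does, unbiopsied PI-RADS 1-2 men are out and the open question is falls in score among men with known cancer.

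Two further inferences are not supported. One is that the phase 2 information sheet is deficient: it is not shown. The other is that such biopsies would distort the study's answer on viability: the phase 1 and phase 2 analyses compare scores, Doppler, volume, lesion size and agreement, and contain no biopsy or workload measure. No view is taken here on which clinical rule is right.

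**What to change.** - Reconcile 1.10.2.2 with 1.5.2, 1.6.1, 1.6.3, 1.6.10 and 1.10.2.3 so that one statement governs biopsy after a study-triggered MRI. It should say which MRI changes it covers and whether the MDT decides. The lead urologist and MDT choose the rule.
- In the same edit, settle whether unbiopsied PI-RADS 1-2 men may enter phase 2.
- State in 1.10.2.1 that taking part may lead to an additional MRI and biopsy, and check that the phase 2 information sheet says the same.

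The cost is a protocol wording amendment and, if the check shows a need, an information-sheet amendment. No procedure, visit or participant is added.

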1.10.2.3 Benefit

The benefit is that the researcher will gain valuable data in terms of stored ultrasound images that can be correlated to previous multi-parametric US, previous existing gold standard MRI and histology where available. The patients will have the satisfaction of participating in a study evaluating new technology which may lead to better outcomes for future patients. The ultrasound imaging is unlikely to be able to provide diagnostic or prognostic information until a comparative analysis with the gold standards has been performed. However, should any findings of incidental pathology or suspicious appearances be determined during the ultrasound examination these will be alerted to the lead clinician. Any such incidental or suspicious findings will then be discussed at the urology MDT to determine a management plan. Such findings may result in early detection of potential issues providing a benefit to participants on this study.

1.10.3 Phase 3

1.10.3.1 Risk

There is minimal risk to health care practitioners participating in phase 3 of the study. There is an established group of sonographers and radiologists providing the radiology prostate cancer assessment care pathway. There is a risk to the study of attrition of participants due to the age

demographics of the available workforce and staff relocating. There is also a risk of conflict between professional groups as knowledge and skills develop. This will be mitigated by regular communication with the study groups, led by the lead researcher and supported by the academic supervisory team as a non-involved third party. The greatest risk however is due to the lead researcher having a pivotal leadership role within the team and crucial to normal service delivery. There is a risk of unintentional bias from participants either feeling they should participate or feeling the need to please. These risks will be mitigated by open and honest communication with all team members upon recruitment and during the study.

1.10.3.2 Burden

There is a burden on the participants in phase 3; this is an additional workload over and above their existing activity. However, the ultrasound department is highly supportive of research and development and allocates time for such activity within practitioners' working day. There is a risk that the radiologists may have competing workloads which cannot be mitigated against but, again, R&D is supported within radiology and this study provides development opportunities for all participants.

1.10.3.3 Benefit

The participants will have the opportunity to learn new skills and improve their knowledge of this common disease. They will be participating in a study with the aim of improving patient care in their chosen field of practice. This will, hopefully, engender professional pride, engagement, and commitment. The participants will have the opportunity to use and experience new ultrasound technology. This study is using the first micro-ultrasound machine installed in the UK and, as such, is ground breaking in the UK knowledge of prostate ultrasound imaging.

1.10.4 Phase 4

Phase 4 of the study requires the organisation of a study event. There will be little in terms of burden on the participants of this event; indeed, it is likely to be hugely beneficial in terms of sharing practice and hearing about new technology. The burden will be on the lead researcher who will be responsible for organising the event and ensuring an accurate record of discussions is transcribed. However, there are benefits of discussion with other health care providers ensuring the research does not become single centre-centric and to provide a wider overview of practice that could be implemented to better improve local services.

1.11 Confidentiality

This project is a prospective study comprising data from the medical records of patients of Hull University Teaching Hospitals NHS Trust, who in keeping with standard clinical care and management, have undergone diagnostic tests, treatments and interventions but who will be consenting to additional diagnostic imaging examinations. Therefore, in accordance with the Health Research Authority (2017), this study requires approval from the Local Research Ethics Committee (LREC). As this study is being undertaken as part of a PhD programme, ethical release has been sought from the University of Hull.

1.12 Approval

Approval from the Hull University Teaching Hospitals NHS Trust will be sought in line with the local Research And Development Operational Policy which is in place to ensure studies adhere to a robust ethical framework. Key to this is legislation in the Data Protection Act (2018), General Data Protection Regulations (Gov.UK, 2018) and the guidance upheld in the Caldicott Principles 1997.

Wherever possible sensitive and personal information, which may identify participants, will be removed to minimize the risk of data breaches. The Hull University Teaching Hospitals NHS Trust data protection policy and procedures will ensure possible data breaches are risk assessed and that protection of network drives are maintained and kept current. Unnecessary data will not be stored.

1.13 Data security

All data will be collected within the following restrictions:

Only the data required for the evaluation of the study aims and objectives will be collected. All data will be accurately transcribed and analysed within the confines of the requirements of the project. The data will be utilised for the specific purpose of this study only. Consent forms will include permission for data access by the primary research team, use of data in publication as well as consent for future studies which may originate from this primary study.

New and emerging technology is used in this study and as such new diagnostic features may become evident. As such intellectual property rights are considered and advice is sought from the Hull University Teaching Hospitals NHS Trust IP team.

1.13.1 Incidental or adverse clinical findings

Consideration is given to incidental pathology or suspicious findings detected as part of the imaging component undertaken during the diagnostic data set collection within this study. The consent

forms will include permission for the researcher to share any abnormal findings or concerns about suspicious findings with the participant's clinical team to avoid unnecessary delay to diagnosis and / or clinical treatment.

1.14 Conflict of interest

[figure not shown]
The major conflict of interest is that the lead researcher is a sonographer and will be going through a period of skill development as per the participants in phase 3 of the study. Robust supervision will mitigate against undue bias during the phase 3 data collection and analysis.

Participants may request access to data relating to their own input into the study and will be given access to their own record only. No other participant data will be shared.

[figure not shown]
